8.5.3. Other Efficacy Endpoints

The following efficacy endpoints will be analyzed from Day 1 to each timepoint up to Week 44, where applicable:

1. Proportion of subjects achieving HiSCR;
2. Proportion of subjects achieving at least 30% reduction and at least 1 unit reduction from Day 1 in subject's global assessment of skin pain (NRS30), in subjects with a Day 1 NRS of at least 3;
3. Proportion of subjects with baseline Hurley Stage II who achieved an abscess and inflammatory nodule count of 0, 1, or 2;
4. Change from Day 1 in inflammatory nodule count, abscess count, draining fistula count, and total AN count;
5. Change from Day 1 in the Sartorius score, modified Sartorius score, IHS4 score, and HS-PGA to quantify the severity change of HS;

6. Change from Day 1 in patient-reported outcomes: SF-36 v2, EQ-5D-5L, HiSQOL, and DLQI;
7. Proportion of subjects who experienced flare, defined as an at least 25% increase in AN counts with a minimum increase of 2 AN lesions relative to Day 1;
8. Duration of flare in days (calculated from the day when flare is observed to the day prior to the observation that flare is no longer present; of note, there could be multiple periods that flares are observed, in which case, the total days from the multiple periods will be used);
9. Proportion of subjects who experience at least 25% increase in draining fistula counts with a minimum increase of 2 draining fistula counts relative to Day 1;
10. During Period 2, Proportion of subjects with a loss of response (LOR), defined as loss of at least 50% of AN count improvement achieved from Day 1 to Week 12;
11. Time to LOR during Period 2;
12. Proportion of subjects who received oral antibiotic rescue therapy;
13. Proportion of subjects who start disallowed opioid pain therapy;
14. Proportion of subjects who undergo lesion intervention due to HS;
15. Number of lesion interventions due to HS;
16. Health-economic information:
 - a. WPAI:SHP: Change from Day 1 to each timepoint during Period 1 and Change from Week 12 to each timepoint during Period 2 and including the follow-up period;
 - b. Hospitalizations (cumulative): Number of Hospitalizations total and due to HS, Number of days hospitalized, Number of days missed from work;
 - c. Emergency or Urgent Care visits (cumulative): Number of visits total and due to HS, Number of days (or hours where applicable) missed from work;

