Continuous variables will be analyzed using a mixed effects model for repeated measures. This model will include treatment group, visit, treatment-by-visit interaction, and randomization strata (Hurley Stage II or Hurley Stage III, previous anti-TNF- α drug use or anti-TNF- α drug naïve, concomitant antibiotic therapy use or not) as factors, and baseline as covariate. Subjects will be considered as repeated measure units over visits. Testing p-values, point estimates and corresponding 95% confidence intervals will be estimated for the difference between the

avacopan group and the placebo control group across 12 weeks using linear contrast from the model.

For the analysis of subject's global assessment of skin pain (NRS30) up to Week 12, subjects who received analgesics or disallowed pain therapy will be counted as non-responder for categorical variables. For continuous variables, LOCF applies. Hereby, the last pain assessment is carried forward from the start day of the analgesics or day of the intervention until 14 days after the stop of analgesic use or day of the intervention. Concomitant medication for treatment of pain will be reviewed. Disallowed pain therapy will be determined by a blinded data review prior to database lock.

The test of 10 mg vs. 30 mg avacopan groups will be conducted at each timepoint for the endpoint of the proportion of subjects achieving HiSCR and the secondary endpoints. A detailed Type I management plan for the secondary endpoint testing will be provided in SAP.

8.8.4. Analysis of Secondary and Other Efficacy Endpoints in Period 2

The efficacy data for secondary and other endpoints by timepoint in Period 2 will be summarized using the mITT2 population. Analysis of other efficacy endpoints will be conducted from Day 1 to each timepoint.

For the analysis of time to loss of response (LOR), the treatment difference between the 10 mg and 30 mg avacopan groups will be analyzed using the stratified log-rank test with baseline randomization stratification factors as the stratification variables.

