The DLQI is calculated by adding the score of each question. The maximum score is 30, and the minimum score is 0. The higher the score, the more quality of life is impaired.

Meaning of DLQI Scores

0-1 = no effect at all on subject's life

2-5 = small effect on subject's life

6-10 = moderate effect on subject's life

11-20 = very large effect on subject's life

21-30 = extremely large effect on subject's life

Change from Baseline in Score = Post Baseline Score - Baseline Score

8) Proportion of subjects who experienced flare, defined by at least a 25% increase in AN counts with a minimum increase of 2 AN counts relative to Baseline

The AN count is the sum of all abscesses and inflammatory nodules counts across all regions.

% Increase in AN counts

$$= 100 \times \frac{\text{(AN Counts at Day x} - \text{AN Counts at Baseline)}}{\text{AN Count at Baseline}}$$

The proportion of subjects who experienced flare at Post Baseline visits will be calculated as those subjects having % Increase in AN counts ≥ 25 and (Post Baseline AN Counts – Baseline AN Counts) ≥ 2 at Post Baseline visits divided by the total number of subjects in each treatment group.

9) Duration of flare in days (Observed case only)

> Duration of flare in days is calculated from the day when flare is observed to the day prior to the observation that flare is no longer present; of note, there could be multiple periods that flares are observed, in which case, the total days from the multiple periods will be used.

10) Proportion of subjects who experience at least 25% increase in draining fistula counts with a minimum increase of 2 draining fistula counts relative to Baseline.

% Increase in Draining Fistula Counts

The proportion of subjects who experienced at least 25% increase in draining fistula counts with a minimum increase of 2 draining fistula counts relative to Baseline at Post Baseline visits will be calculated as those subjects having % Increase in Draining Fistula Counts > 25 and

(Post Baseline Draining Fistula Counts —

Baseline Draining Fistula Counts) ≥ 2 at Post Baseline visits divided by the total number of subjects in each treatment group.

11) During Period 2, proportion of subjects with a loss of response, (LOR) defined as loss of at least 50% of AN count improvement achieved at Week 12 from Period 1.

AN in Period 2 – Week 12 AN $> \frac{1}{2}$ (Baseline AN – Week 12 AN)

i.e., AN in Period 2 > $\frac{1}{2}$ (Baseline AN +Week 12 AN)

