Proportion of subjects with a LOR in Period 2 is calculated as those subjects having AN Counts in Period 2 $> 0.5 \times$ (Baseline AN counts —Week 12 AN counts) divided by the total number of subjects in each treatment group in Period 2.

12) Time to LOR during Period 2.

For subjects with LOR, time to LOR (days) = date of LOR – date of the first dose of study drug in Period 2 + 1; For Subjects without LOR or lost follow-up, subjects will be censored at the date of the last assessment of number of HS lesions, i.e., time to LOR (days) = date of last assessment of number of HS lesions – date of the first dose of study drug in Period 2 + 1.

 Proportion of subjects who received add-on antibiotic or other therapy for HS during Period 1 and Period 2 separately.

Add-on antibiotic or other therapies for HS are captured in the Concomitant Medication CRFs.

Proportion of subjects who received add-on antibiotic or other therapy will be calculated as those subjects who received add-on antibiotic or other therapy documented in the CM CRF post baseline divided by the total number of subjects in each treatment group in the safety population.

14) Proportion of subjects who start disallowed opioid pain therapy during Period 1 and Period 2 separately.

Oral and transdermal opioid analgesics (except for tramadol) for any reason are disallowed. Disallowed opioid pain therapy are captured in the Concomitant Medication (CM) CRFs.

Proportion of subjects who start disallowed opioid pain therapy will be calculated as those subjects who start disallowed opioid pain therapy documented in the CM CRF post baseline divided by the total number of subjects in each treatment group in safety population.

15) Proportion of subjects who undergo lesion intervention due to HS during Period 1 and Period 2 separately.

Lesion intervention due to HS is collected in AE and Concurrent Procedures CRFs.

Only two types of interventions are allowed: injection with intralesional triamcinolone acetonide suspension (intralesional Kenalog® rescue injections, i.e., triamcinolone acetonide, 10 mg total maximum per subject within a period no longer than 1 week) and incision and drainage. Any disallowed lesions interventions due to HS other than the two types described above will also be counted as "Lesion intervention due to HS" and will be recorded as major (=CSR reportable) protocol deviation.

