For the analysis of time to loss of response (LOR), the treatment difference between the avacopan 30 mg vs. placebo to avacopan 30 mg, avacopan 10 mg vs. placebo to avacopan 10 mg, avacopan 30 mg group vs. avacopan 10 mg group, and placebo to avacopan 30 mg vs. placebo to avacopan 10 mg will be analyzed using the stratified log-rank test with the baseline Hurley Stage (Stage II vs. III), concomitant antibiotic therapy with allowed antibiotics (Yes vs. No), and anti-TNF drug use (Treatment naïve vs. Previous treatment) as the stratification variables. Subjects without LOR or lost follow-up will be censored at the date of the last assessment of number of HS lesions. Kaplan-Meier curves will be provided by treatment group.

IX. Safety Analyses

Safety analyses will be performed in the Safety Analysis Set using the actual treatment group.

A. Adverse Events

All subjects will be assessed regularly for potential occurrence of adverse events (AEs) throughout the study until the subject is off study. The Medical Dictionary for Regulatory Activities (MedDRA; Version 21.1) will be used to code all adverse events to a System Organ Class (SOC) and Preferred Term (PT).

A treatment-emergent AE (TEAE) in Period 1 is defined as any AE that occurs after the first dose of study treatment in Period 1 and before the date of first dose of study treatment in Period 2.

A treatment-emergent AE (TEAE) in Period 2 is defined as any AE that occurs after the first dose of study treatment in Period 2.

A treatment-emergent AE (TEAE) for all avacopan, is defined as any AE that occurs after the first dose of avacopan treatment in study.

The incidence of TEAEs will be summarized and tabulated by treatment group and period.

The severity of each AE will be assessed as mild, moderate, severe, lifethreatening, fatal, or death. Several occurrences of the same AE in one subject will be counted once and the one with maximum severity will be counted.

The relationship of each AE to the blind study medication will be classified as probably not related or possibly related. Several occurrences of the same AE in one subject will be counted once and the one with the maximum relationship to blind study medication will be counted. If an AE is missing the relationship to blind study medication, the event will be assumed to be probably related for analysis and summarization.

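### The SAP's time-to-LOR tests of continued versus switched avacopan use a threshold set on drug in one arm and on placebo in the other, so they do not measure durability, and the bias can run either way

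*SAP*

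**What the plan says.** SAP VIII.E.2 (Period 2 analyses) applies stratified log-rank tests to time to LOR for four pairs. Two compare continued with switched subjects at the same dose: "avacopan 30 mg vs. placebo to avacopan 30 mg, avacopan 10 mg vs. placebo to avacopan 10 mg". The other two are 30 mg against 10 mg in subjects on avacopan throughout, and placebo-to-30 mg against placebo-to-10 mg. The strata are the three baseline randomisation factors; Week 12 AN is not adjusted for. Protocol 8.8.4 planned one comparison: "the treatment difference between the 10 mg and 30 mg avacopan groups will be analyzed using the stratified log-rank test". SAP Section X does not list the added pairs as a change.

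Protocol 8.5.3 item 10 has LOR "defined as loss of at least 50% of AN count improvement achieved from Day 1 to Week 12". SAP VIII.B, Other Efficacy Endpoints item 11, words it as "loss of at least 50% of AN count improvement achieved at Week 12 from Period 1" and reduces it to Period 2 AN above ½ × (Baseline + Week 12). The next sentence, which defines the proportion, prints ½ × (Baseline − Week 12) instead. That proportion is "divided by the total number of subjects in each treatment group in Period 2", with no requirement that a subject improved by Week 12. In item 12, time to LOR is the event date minus the "date of the first dose of study drug in Period 2 + 1".

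SAP VI.I classes other endpoints as supportive or exploratory, tested at two-sided 0.05 without multiplicity adjustment.

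**The concern.** A loss-of-response comparison should ask whether a response, once gained on the drug, is kept. In the continued arm the reference is 12 weeks of avacopan. In the switched arm it is 12 weeks of placebo, and active drug then begins just as the clock starts. The event is thus defined by a post-randomisation value that depends on treatment, and the two arms do not share the same event. A nominal p below 0.05 could be read as waning of effect on continued avacopan, or as proof of durability, when it reflects neither.

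**Working it through.** **1. The plan's own figures.** Neither document gives power, event counts or a hazard ratio (HR) for LOR. The stated power is for HiSCR: 30% vs 50%, 130 per arm, two-sided 0.05, about 90% (Protocol 8.3, SAP IV.C). With n per arm and pooled p = 0.40, power = Φ{[0.20 − 1.96·√(2·0.40·0.60/n)] / √[(0.30·0.70 + 0.50·0.50)/n]}.
- n = 130: (0.20 − 1.96 × 0.06076)/0.05948 = 1.360, giving 91.3%.
- n = 130 × 0.93 ≈ 121: (0.20 − 1.96 × 0.06298)/0.06166 = 1.242, giving 89.3%.

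The stated figure is reproduced. The 30% and 50% rates calibrate the hazard ratios in step 4. Re-randomising placebo 1:1 leaves about 65 switched subjects per dose, or 60 after 7% attrition.

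**2. The midpoint rule by hand.** Threshold = ½(B + W), where B is Baseline and W is Week 12 AN. Room above Week 12 = ½(B − W). Take B = 20.
- Continued subject, W = 10: threshold 15. Switched subject, W = 16: threshold 18. If their Period 2 disease is identical, a count of 16, 17 or 18 is LOR for the first and not for the second.
- Room also grows with improvement: W = 4 leaves 8 lesions, W = 16 leaves 2. This pulls the other way.
- With no improvement there is no room: W = 20 gives 0. W = 24 gives −2 (threshold 22), so a count that stays at 24 is LOR at the first Period 2 visit. Such subjects are more common after placebo: in simulation, 52-68% improved on placebo against 72-85% on drug.

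**3. The second formula.** A loss of more than half the improvement is AN − W > ½(B − W), which rearranges to AN > ½(B + W). The other printed version, AN > ½(B − W), does not follow from the definition. Under it, a subject who simply stays at W has LOR whenever W > ½(B − W), that is W > B/3. With B = 20 and W = 10, an exact 50% responder who stays at 10 exceeds the threshold of 5.

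**4. Simulated hazard ratios.** Assumptions not in the documents:
- baseline AN at least 5, mean about 11;
- between-subject SD of the log ratio 0.4 or 0.7, visit-to-visit SD 0.2 to 0.6;
- six visits, Weeks 16 to 36;
- drug effective in 40%, 60% or 100% of subjects;
- continued arm stays at its Week 12 level;
- unstratified log-rank, all subjects.

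HR is continued over switched; above 1 means continued drug looks worse.

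| Onset in switched arm | HR, midpoint rule |
|---|---|
| at once | 1.20 to 1.59 |
| linear over 12 weeks | 1.02 to 1.17 |
| delayed, or over 24 weeks | 0.81 to 0.94 |
| no drug effect | 1.00 |

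The second formula, read literally, gives 0.75 to 0.93.

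**5. Simulated rejection rates, drug effect fully maintained.**
- 121 vs 60, SDs 0.7 and 0.4, drug effective in all: 48.8% against continued drug with immediate onset (LOR about 65% vs 51%) and 8.8% with 12-week onset. Replacing the midpoint by a threshold fixed on baseline (AN above 75% of baseline, for illustration) cuts these to 2.1% and 0.05%, which points to the reference as the cause.
- 120 vs 60, Poisson counts around mean 12, 50% fall on drug, 20% on placebo, all subjects: 49-52% against with immediate onset and 5-8% with 12-week onset. With 24-week onset, 16% favour continued drug.
- Same model, only subjects improved at Week 12, placebo fall 20-30%: 18-39% against with immediate onset and 5-6% with 12-week onset. With 24-week onset, at most 0.5% are against and 7.5-11% favour continued drug. With no drug effect, 4-5% reject.
- Second formula, all subjects, immediate onset, 20% placebo fall: 0.0% against, 34.7% in favour of continued drug.

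**The case against.** A reader might infer that an effective avacopan must look worse on this test, so that the p-value is the Period 1 benefit with its sign reversed. The documents do not support that. The inference needs the switched arm to have the full 12-week drug effect by its first Period 2 visit at Week 16. Protocol 1.2 reports rapid onset in ANCA-associated vasculitis, but neither document gives onset data in HS. With 12-week onset the distortion is small, and with slower onset it changes sign. It also changes sign under the SAP's second formula. This objection stands against any claim of direction. It does not rescue the tests, because a p-value whose bias changes sign with an unknown onset speed cannot be interpreted as durability.

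Two further objections have weight. First, time to LOR is an other efficacy endpoint, nothing is gated on it, and Kaplan-Meier curves by group are already planned. That limits the consequence. Second, the 30 mg versus 10 mg comparison also uses a reference that depends on treatment. That is true, but neither arm changes treatment at Week 12, so each subject is judged against a response gained on the regimen still being taken. It needs a caveat rather than removal.

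**Conclusion.** The point holds as a confounded comparison of unknown direction. What follows from the documents alone is that the two same-dose tests are in the SAP and not in the protocol, that the reference is set on avacopan in one arm and on placebo in the other, that nothing adjusts for it, and that two incompatible LOR formulas are printed. These facts are enough to say that the log-rank result does not measure durability of avacopan response.

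The size rests on the simulation assumptions above and is not an estimate for this trial. With rapid onset, roughly 20-50% of trials falsely reject against continued drug. With about 12-week onset the figure is 5-9%. With slower onset, or under the second formula, the error favours continued drug. The effect on the trial's conclusions is limited because the endpoint is exploratory.

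**What to change.** Revise the SAP before the Period 2 analysis:
- Remove the two same-dose continued-versus-switched log-rank tests from VIII.E.2 and show those Kaplan-Meier curves descriptively.
- Keep placebo-to-30 mg against placebo-to-10 mg. These subjects are re-randomised after the reference is fixed, so the arms are comparable.
- Keep the protocol's 30 mg against 10 mg test, with a note that its reference depends on dose.
- Reconcile the two formulas in VIII.B item 11 (Baseline + Week 12 against Baseline − Week 12), and use one definition for both the proportion and the time to LOR.
- State how subjects with no Week 12 improvement are handled, since the midpoint rule can call an unchanged count a loss of response.
- Record the change to the LOR comparisons in Section X.

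The cost is wording and two exploratory p-values. SAP VIII.E.2 already plans baseline-adjusted repeated-measures contrasts of each continued dose against the pooled switched group on selected endpoints, so little information is lost.

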 a. WPAI:SHP: Change from Baseline to each timepoint during Period 1 and Change from Week 12 to each timepoint during Period 2 and including the follow-up period; Work Productivity and Activity Impairment Questionnaire (WPAI:SHP) assesses the effect of general and specific health conditions on productivity losses. Scores are calculated for four areas: percent work time missed due to HS, percent impairment while working due to HS, percent overall work impairment due to HS, and percent activity impairment due to HS. Forms for this instrument will be completed by study subjects at visits specified in the Time and Events Table to measure changes from baseline in work productivity and activity impairment.

 Hospitalizations (cumulative) by period: Number of Hospitalizations total and due to HS, Number of days hospitalized, Number of days missed from work.

Hospitalizations are captured in Heath Economics Information CRFs, cumulative number will be calculated by sum of the numbers from each visit.

 Emergency or Urgent Care visits (cumulative) by period: Number of visits total and due to HS, Number of days (or hours where applicable) missed from work.

Emergency or Urgent Care visits are captured in Heath Economics Information CRFs, cumulative number will be calculated by sum of the numbers from each visit.

d. Lesion interventions for HS by period: Number of days (or hours where applicable) missed from work due to HS lesion interventions.

Lesion interventions for HS are captured in Heath Economics Information CRFs, cumulative number of days missed from work due to HS lesion interventions will be calculated by sum of the numbers from each visit.

C. General Approach

Lesions that received intervention (incision and drainage, or intralesional injection of corticosteroid) will be counted as permanently present from the date of the intervention.

In order to adjust for the impact of major protocol disallowed treatments on the results of the trial, efficacy assessments obtained after the start of major protocol disallowed treatments will be excluded from the analysis (unless otherwise specified). Subject will be counted as non-responders for the categorical variables and have their last observation carried forward for continuous variables.

Concomitant therapy that would qualify as a rescue medication will be reviewed prior to database lock.

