- The Work Productivity and Activity Impairment Questionnaire: Specific Health Problem (WPAI:SHP), change from baseline to Week 12 (MMRM model, ANCOVA model)

For the other endpoints, only the primary analysis will be applied.

For the analysis of variables in Period 1, not by visit, such as: duration of flare, health-economic information on hospitalizations, emergency or urgent care visits,

and lesion interventions for HS, an analysis of covariance (ANCOVA) model with treatment, baseline value, Hurley Stage (Stage II vs. III), concomitant antibiotic therapy with allowed antibiotics (Yes vs. No), and anti-TNF drug use (Treatment naïve vs. Previous treatment) will be applied. Treatment comparisons between the avacopan group and the placebo control group will be presented.

2. Analysis of Secondary and Other Efficacy Endpoints in Period 2

The efficacy data for secondary and other endpoints by timepoint in Period 2 will be summarized using descriptive statistics in the ITT2 population.

For binary variables, Non-Responder Imputation will be used; for change from baseline variables, other than lesion counts endpoints, no missing data imputations will be performed.

For selected secondary efficacy endpoints specified above, a MMRM model including treatment group, visit, treatment-by-visit interaction, and randomization strata (Hurley Stage II or Hurley Stage III, previous anti-TNF-α drug use or anti-TNF-α drug naïve, concomitant antibiotic therapy use or not) as factors, and corresponding baseline as covariate will be applied in Period 2. Testing p-values, point estimates and corresponding 95% confidence intervals will be estimated for the difference the avacopan 30 mg vs. total placebo to avacopan group, and avacopan 10 mg vs. total placebo to avacopan group across visits in Period 2 using linear contrast from the model.

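### Time to loss of response: a subject who starts a disallowed HS treatment in Period 2 is censored and never counted as an event, unlike under the SAP's own non-responder rule

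*SAP*

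**What the plan says.** SAP VIII.B, Other Efficacy Endpoints, item 11 gives the Period 2 endpoint as "proportion of subjects with a loss of response, (LOR) defined as loss of at least 50% of AN count improvement achieved at Week 12" and writes it as an inequality: Period 2 AN count above half the sum of the baseline and Week 12 counts. LOR depends on lesion counts alone, as in Protocol 8.5.3.

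Item 12 measures time to LOR from the first Period 2 dose and adds: "For Subjects without LOR or lost follow-up, subjects will be censored at the date of the last assessment of number of HS lesions". SAP VIII.E.2 repeats this: "Subjects without LOR or lost follow-up will be censored at the date of the last assessment of number of HS lesions". It plans four stratified log-rank comparisons and Kaplan-Meier curves.

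SAP VIII.C sets the general rule for other treatment: "efficacy assessments obtained after the start of major protocol disallowed treatments will be excluded from the analysis", unless something else is specified. The consequence follows: "Subject will be counted as non-responders for the categorical variables and have their last observation carried forward for continuous variables". For Period 2, VIII.E.2 adds: "For binary variables, Non-Responder Imputation will be used".

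None of these passages says what a major disallowed treatment does to a time-to-event variable. No competing-event or sensitivity analysis is given for time to LOR.

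**The concern.** Subjects normally turn to another HS treatment because their disease is getting worse. Censoring at that point assumes that they would have gone on to lose response at the same rate as those who stayed on study drug alone, which is doubtful. If so, the Kaplan-Meier curves make response look more durable than it is.

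The documents leave room for such cases. Protocol 4.4 keeps subjects who take prohibited medication in follow-up. Protocol 5.7 bars starting a systemic antibiotic for HS, with rescue at Week 4 or 8 only. Protocol 3.3 describes a short rescue course for flares without tying it to those visits, so which Period 2 antibiotic starts are disallowed is not fully settled and those sections must be reconciled.

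The SAP also has two LOR endpoints, a proportion and a time. If the non-responder rule makes a starter a failure in the proportion, the same subject is a failure in one and censored in the other. Time to LOR is the planned Period 2 test of durability, and one of its comparisons is 30 mg against 10 mg.

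**Working it through.** **Step 1. Follow one subject through the text.** The subject starts a major disallowed HS treatment in Period 2 before the AN threshold is passed.
- VIII.C removes later lesion counts. Items 11 and 12 define LOR by lesion count only, so no later LOR can be recorded.
- If the last assessment means the last retained one, the subject is censored when the other treatment starts. If it means the last visit attended, the subject stays event-free while on the other treatment. Neither reading produces an event.
- In the LOR proportion, VIII.C and the Period 2 imputation rule make the subject a non-responder. For an adverse outcome this most naturally means LOR = yes, but item 11's numerator lists only subjects who pass an AN threshold.

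**Step 2. Inputs.** The documents give no LOR rate, event count or power for this endpoint. The only stated design figure is about 90% power for HiSCR (Protocol 8.3; 30% against 50%, two-sided 0.05). With pooled variance, power is Φ[(0.20√n − 1.96√0.48)/√0.46]. This gives 91.3% at n = 130 and 89.3% at n = 121, so the figure reproduces, but it does not bear on LOR. It supplies only the arm size: 130 × 0.93 ≈ 121.

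Assumptions: 30% LOR over 24 weeks (range 20% to 40%), and an observed share s of 3% to 10% starting a disallowed treatment first. SE ≈ √(0.30 × 0.70/121) = 4.2 points.

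**Step 3. Censoring against counting as failure, independent constant hazards.** Let H = −ln(0.70) = 0.357, and let G solve [G/(H+G)] × [1 − exp(−(H+G))] = s. One minus Kaplan-Meier stays at 30%. The composite is 1 − exp(−(H+G)).

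| s | G | Composite | Gap in SE |
|---|---|---|---|
| 3% | 0.036 | 32.5% | 0.6 |
| 5% | 0.061 | 34.2% | 1.0 |
| 8% | 0.100 | 36.6% | 1.6 |
| 10% | 0.126 | 38.3% | 2.0 |

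With 3% starters the gap is 0.74 SE at 20% LOR and 0.52 SE at 40%. Because the hazards are independent here, Kaplan-Meier is unbiased for LOR without other treatment. The gap is a difference between two estimands.

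**Step 4. Bias when the two event times are positively related.** Use a shared gamma frailty of variance θ (an assumption). L = (0.70^(−θ) − 1)/θ keeps the true LOR risk at 30%. D solves [D/(L+D)] × [1 − (1+θ(L+D))^(−1/θ)] = s. Then one minus Kaplan-Meier = 1 − (1+θ(L+D))^(−L/(θ(L+D))). The shortfall from 30%, in units of 4.2 points, is:

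| θ | s = 3% | 5% | 8% | 10% |
|---|---|---|---|---|
| 0.5 | 0.05 | 0.09 | 0.14 | 0.18 |
| 1 | 0.10 | 0.16 | 0.26 | 0.33 |
| 2 | 0.17 | 0.29 | 0.47 | 0.59 |

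**Step 5. Between arms.** Take equal LOR hazards (30%) and assume net disallowed use of 20% on 10 mg and 5% on 30 mg. The hazard ratio is 1.00 with censoring. With starters counted it is (0.357 + 0.051)/(0.357 + 0.223) = 0.70. With equal use, both are 1.00.

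**Step 6. The two printed thresholds.** Item 11's inequality uses ½(Baseline + Week 12). The proportion formula below it uses 0.5 × (Baseline − Week 12). For an AN count falling from 20 to 8, these are 14 and 6. A subject who simply stays at 8 has LOR by the second (8 > 6) and not by the first (8 < 14).

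**The case against.** The strongest reply is that censoring at other treatment is a recognised choice. It targets LOR had no other treatment been taken, and counting starters as failures changes an endpoint that the protocol defines by AN count alone. That stands as a description of the estimand. But the SAP does not say it wants that estimand, and it uses the opposite convention for categorical variables.

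A reader might infer from Step 3 that the Kaplan-Meier estimate is biased by more than half an SE once about 3% of subjects start another treatment. The documents and the arithmetic do not support that. Step 3 compares two quantities. The bias in Step 4 is at most 0.17 SE at 3%, and passes half an SE only at 10% with the strongest dependence tried.

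A reader might also infer that the dose comparison is distorted. That needs different starter rates between arms. In Period 2 every group receives avacopan with the dose undisclosed, and nothing in the documents points to a difference.

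Three further points stand. Lesions treated by incision and drainage or injection are counted as permanently present, so that route still counts toward LOR. The number of major disallowed treatments is unknown, since concomitant therapy is reviewed before database lock. And the risk set may be smaller than 121: if only half could lose a response, the SE is √(0.21/60.5) = 5.9 points, and the 2.5-point gap at 3% starters is 0.42 SE.

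**Conclusion.** The point holds as a gap in the rules. On any reading of VIII.B item 12, VIII.C and VIII.E.2, a move to another HS treatment is never an event for time to LOR, and the resulting censoring is likely to be informative. It is tempting to say that the LOR proportion counts these same subjects as failures. That is the natural reading, but it is an inference, because item 11 does not state it.

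The size cannot be fixed from the documents. Under the assumed 30% LOR and 3% to 10% starters, the choice of rule moves the estimate from 30% to about 32% to 38%, and bias under assumed positive dependence is about 0.05 to 0.6 SE. Arms are affected differently only if starter rates differ.

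Time to LOR is one of the other efficacy endpoints, which SAP VI.I calls supportive or exploratory with no multiplicity adjustment. The primary and ranked secondary conclusions are unaffected. The conflict between the two LOR thresholds rests on no assumption and needs correcting in any case.

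**What to change.** In SAP VIII.B item 12 and VIII.E.2:
- Count the start of a major disallowed HS treatment in Period 2 as LOR on its start date, in line with VIII.C. The event date is then the earlier of that date and the first visit above the AN threshold.
- Keep the present censoring, or a cumulative incidence function with other treatment as a competing event, as a sensitivity analysis.

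In VIII.B item 11:
- State that non-responder means LOR = yes in the LOR proportion.
- Reconcile the threshold ½(Baseline + Week 12) with the formula 0.5 × (Baseline − Week 12).

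The cost is SAP wording, one derived date and one extra analysis. Other HS therapies are already captured on the concomitant medication form. The downside is that LOR estimates rise slightly and the endpoint becomes a composite, which the report should say.
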